## Johns Hopkins Medicine - eForm A

### 1. Abstract

The purpose of this pilot study is to investigate the use of deep brain stimulation (DBS) of the medial thalamus in 10 subjects with treatment-resistant Tourette Syndrome (TS). Tourette Syndrome is a type of tic disorder with a prevalence of 1-10 per 1000, and in its milder forms can affect 0.6% of the population (1). Patients with Tourette Syndrome also suffer from other psychopathologies including obsessive-compulsive disorder (OCD), attention deficit hyperactivity disorder (ADHD), learning difficulties, and sleep abnormalities (1). Treatment for Tourette Syndrome includes nonpharmacologic interventions such as behavioral therapy, habit reversal technique, and comprehensive behavioral intervention (CBIT) for tics (1). First line medication therapy includes drugs such as clonidine, guanfacine, and topiramate, and failing these often atypical and typical neuroleptics are tried. For patients failing medical therapy, deep brain stimulation has been used at a few centers (2-4). DBS is in other early phase clinical trials in other psychiatric disorders such as treatment-resistant depression and early results are promising.

This pilot study will investigate the use of DBS in treatment-resistant Tourette Syndrome who have exhausted all other therapeutic alternatives but continue to have persistent disabling tics. Of note, DBS is not FDA approved for use in patients with Tourette Syndrome. The method will be similar to that used in thalamic deep brain stimulation in patients with Essential Tremor. However, the electrode will be placed in a different region of the thalamus, namely the region of the centromedian nucleus, substantia periventricularis, and the nucleus ventro-oralis interna (Ce-Spv-Voi, Hassler nomenclature) (5,6). The choice of this target was guided by results from early lesioning studies (7), and by the role of the ventral thalamic nuclei as elements with strong projections to prefrontal cortex and striatum which are regions known to be involved in the pathophysiology of the disease (8). Frequent monitoring and clinical assessment with psychiatric scales will be used to monitor the treatment response.

There is a subset of patients with TS who continue to have persistent tics despite multiple adequate medication trials with appropriate medical therapy. There are currently no available treatments for such patients who generally have poor function and are chronically disabled, unable to work, live independently or have meaningful social relationships. Neuroimaging studies in patients with TS have revealed information about pathological neural circuits that could be suitable targets using deep brain stimulation (9,10,11,12,13).

### 2. Objectives (include all primary and secondary objectives)

#### 2.1. Primary Objectives

- To evaluate the efficacy of DBS of the thalamic Ce-Spv-Voi complex on tic frequency and severity in 10 subjects with treatment-resistant Tourette Syndrome.
- To evaluate the safety of DBS of the thalamic Ce-Spv-Voi complex in 10 subjects with treatment-resistant Tourette Syndrome.

#### 2.2. Secondary Objectives

- To evaluate the efficacy of DBS of the Ce-Spv-Voi complex on cognitive symptoms in 10 subjects with treatment-resistant Tourette Syndrome and any other concurrent psychopathologies including obsessive-compulsive disorder, and attention deficit hyperactivity disorder.

Date: 2/24/2021  
Principal Investigator: [name], PhD  
Application Number: NA\_00073086

### 3. Background

DBS has been used successfully for the treatment of patients with treatment-resistant movement disorders such as Parkinson's Disease (PD) (14), tremor (15) and dystonia (16). Stimulation of electrodes implanted in deep brain structures modulates activity in brain circuits leading to symptom improvement. More recently, DBS has been proposed as a therapeutic alternative for patients with treatment-resistant depression after scientists observed that the subgenual cingulate region (Brodmann area 25) is overactive in patients with depression refractory to traditional treatments such as antidepressants and electroconvulsive therapy (17). DBS is unique among neurosurgical techniques in that it can easily be studied in a placebo-controlled study design; patients can serve as their own controls in crossover designs in which the stimulator is turned on or off in a blinded fashion. Controlled trials of DBS in depression are currently ongoing. Additional benefits of DBS include that unlike ablative surgery, DBS is reversible and produces little to no tissue damage (18). Because of these advantages, investigators at Johns Hopkins plan to develop a protocol for DBS to target tics in patients with treatment-resistant Tourette Syndrome (defined as patients with persistent tics that have not responded to front-line medical agents such as clonidine, guanfacine, or topiramate). In addition, the intended DBS target may also affect other concurrent psychopathologies such as ADHD or OCD (1).

#### 3.1 Target Choices

Data from neuroimaging studies in patients with TS converge on the finding that TS could involve the dysfunction of cortico-striato-pallido-thalamo-cortical (CSPTC) neural circuits. Thus, modulation of circuit dysfunction with DBS has the potential to be an important treatment modality for patients with medically refractory TS. In a seminal paper summarizing a body of research on CSPTC neural circuits, Alexander, DeLong and Strick described parallel, segregated basal ganglia circuits that share common neuroanatomical characteristics: each involve excitatory glutamatergic projections of multiple areas of the cortex in a topographically organized fashion to part of the striatum, the major input area of the circuit (19). Similar to the development of deep brain stimulation for affective disorders and movement disorders, the targeting choices for the DBS treatment of TS include elements of the CNS linked in a widely connected system. Guided by the original lesioning studies of Hassler and Dieckmann (7), the Maastricht group has focused on stimulation of three separate thalamic regions, namely the centromedian nucleus (representing an intralaminar nucleus), the midline substantia periventricularis, and the nucleus ventro-oralis internus (Voi) (8). Possible mechanisms for efficacy of this stimulation target include the role of the ventral nuclei as elements in the CSTC loops as well as the projections from the midline and intralaminar nuclei to prefrontal cortex and the striatum all of which are thought to be involved in the pathophysiology of the disease (8). GPi has also been proposed as a treatment target as well since it acts as a modulatory element on this circuitry (8,20). And since TS is so often associated with OCD, anterior internal capsule is also being considered (4,20). Unfortunately, there are no animal models for TS, so electrophysiological characterization of the structures involved have been difficult and targeting guidance less well justified (4).

An excellent review of the history of lesioning procedures in TS has been provided by Temel and Visser-Vandewalle (8). Some of the more recent and commonly used targets have been the set of thalamic nuclei described by Hassler and Dieckmann in 1970 (7, 21, 22). This procedure included bilateral lesions in the centromedian nucleus, the substantia periventricularis (a midline thalamic nucleus), as well as the nucleus ventro-oralis internus (Voi). Substantial improvements in tic number and frequency occurred in the lesioned patients (7, 21, 22). In addition to the limbic leucotomy and anterior capsulotomy described above for the treatment of TS (23,24,25), other authors have attempted lesioning bilateral dentate nuclei (26),

Date: 2/24/2021

Principal Investigator: [name], PhD

Application Number: NA\_00073086

performing a cingulotomy in the context of TS coupled with severe OCD (27), lesioning the infrathalamic region (28,29), and even combinations of thalamic and zona incerta lesioning(30). Many of the patients undergoing perithalamic lesioning outside of the set of nuclei described by Hassler and Dieckmann were reported to have decreases in TS symptoms but most had substantial side effects as well (8).

### **3.2 Initial Stimulation Data**

Early clinical reports on the effectiveness of DBS for TS included those of the Dutch Flemish Tourette Surgery Study Group (2, 5) with bilateral thalamic stimulation, as well as a case of bilateral GPi stimulation for refractory TS by Diederich et al. (3). In these two reports, there were substantial reductions in the numbers and frequencies of tics and compulsive behavior (2, 3). Additionally, Flaherty et al. recently published a case of a patient with TS undergoing bilateral anterior internal capsule DBS placement (with the last electrode in the nucleus accumbens.) At 18 months of follow-up the patient demonstrated significant reductions in tic frequency and severity as well (4). A series of 5 patients with TS were examined in a double-blind fashion by Maciunas et al. after undergoing bilateral DBS placement at the Visser-Vandewalle target in the medial and ventral thalamus (31). Four stimulation states were examined in a blinded fashion, including either unilateral stimulation, both on, or no stimulation. The bilateral stimulation state showed statistical improvements in motor and vocal tic numbers and other TS symptom inventories, with 3/5 patients exhibiting marked improvement (31). Additionally, Servello et al. reported on 18 patients undergoing bilateral thalamic stimulation in the same target for refractory TS. These patients demonstrated significant improvements as well up to 18 months of follow-up (32). And more recent positive results were obtained by Ackermans et al. using the thalamic Ce-Spv-Voi complex target in a small double-blind trial involving six patients (6). This group demonstrated a 37% improvement in the Yale Global Tic Severity Scale between DBS on and off states.

## **4. Study Procedures/Overview of Study Design**

### **4.1. Overview of Study Design**

This study is an open-label pilot study to determine the feasibility of DBS of the thalamus (Ce-Spv-Voi complex) in 10 subjects with treatment-resistant Tourette Syndrome (TS). After subjects are determined to have decision-making capacity by an independent psychiatrist or neurologist who is not a member of the study team, they will come in for 3 consecutive baseline visits and will be evaluated by two different study physicians (psychiatrist and/or neurologist) to determine that he/she has a diagnosis of TS. TS symptom scales will be performed at each visit. Subjects who are eligible will undergo a pre-operative diagnostic MRI along with a planning stereotactic planning MRI, and will undergo neurosurgical implantation of the DBS device followed by implantation of a neurostimulator under the chest wall. Subjects will be monitored at Weeks 1, 2, 3, 4 and then at Months 3, 6, 9 and 12 after implantation of the neurostimulator. At each visit, subjects will be assessed for adverse events and will undergo routine procedures for monitoring patients who undergo DBS, including recording concomitant medications, optimization of stimulation parameters, TS symptom scale assessments to document changes in symptoms, and neuropsychological assessment to document any changes in cognition. No blinding will be performed. Subjects will continue their pre-surgical psychiatric medications and any changes in medications will be documented at each study visit.

The subjects will be followed for one year after implantation. We estimate three implantations per year will be performed, implying just over three years required to complete the implantations. We estimate the full

Date: 2/24/2021

Principal Investigator: [name], PhD

Application Number: NA\_00073086

study duration to be 5-6 years to complete the initial 13 Visits for all of the subjects, prior to the long-term follow-up segment of the study which involves visits approximately semiannually for 2 years followed by annually for the duration of device implantation.

Because this study is being conducted on a vulnerable clinical population, an independent psychiatrist that is not a member of the investigational study team with experience in capacity assessments will assess the decision-making capacity of each potential subject prior to any study-related activities.

If the subject is found to have capacity to provide informed consent, prior to any study-related activities, the subject must provide written informed consent. The PI explains the study (characteristics of the DBS device and neurosurgical procedure for implantation, required procedures, potential hazards, and possible adverse reactions) to all prospective participants. The PI will maintain each subject's Informed Consent Form, signed and dated by the subject and the PI, in the subject's file.

Movement assessments will be videotaped during the clinical examinations. The videotapes will be utilized for clinical, research, and teaching purposes. Since the movements and expressions of the face are crucial to the characterization of the motions and emotions of the subject, the face and eyes of the subjects will be included in the videotapes. Videotapes may also be utilized for clinical, research, and teaching purposes. Portions of videotapes may be presented at professional conferences and published in hard copy and online journals. The names and all identifiers of the subjects will be deleted from all videotapes before presentation or publication.

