#### **4.10. Visit 13 – Study Completion (or Early Termination Visit)**

This visit is approximately 4 months after Visit #12.

The purpose of this last visit is to monitor for symptom changes, report any complications and to optimize programming if necessary. Subjects will come in at 4 months after the last visit (12 months after implantation of the neurostimulator). The study neurologist experienced in programming in conjunction with one of the study psychiatrists will use TS symptom scales (YGTSS, YBOCS, and the WHO Adult ADHD Self-Report Scale), acute changes in depression or anxiety symptoms, and appearance of adverse events deemed likely to be related to DBS to optimize programming at all subsequent follow-up visits.

The following assessments will be conducted at study completion (or if the subject is early terminated from the study for any reason):

- Programming Form
- New/changed adverse events
- Record changes in concomitant medications
- TS symptom scales (YGTSS, YBOCS, and the WHO ASRS)
- Ham-D, BAI, YMRS (Beck Youth Inventory for ages 15-17)
- GAF
- Neurocognitive battery (as per Visit #1)

At the conclusion of this visit, the subject will be discharged from the study and will continue standard clinical care for patients who undergo DBS procedures. The patient will continue to meet with the study physicians. If symptom improvement has been observed with DBS, the patient will continue standard of care for DBS. If symptom improvement has not been observed, the subject can opt to have the stimulation device turned off.

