## **7. Study Statistics**

### **7.1. Primary Outcome Variable – Efficacy**

The primary outcome variable will be the clinical response of tic symptoms to treatment, as defined by a 40% decrease from baseline in the Yale Global Tic Severity Scale. The cutoff of 40% was chosen to be consistent with the lower end of improvements observed in previous drug trials treating TS when compared to placebo (1). An improvement in at least one of the three participants is a potential indicator that DBS implantation in treatment refractory Tourette Syndrome can be pursued further.

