### **7.4. Statistical Plan**

This is a pilot study looking at using DBS in 10 Tourette Syndrome patients.

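### The plan does not say how a tic drug started or increased after implantation affects the 40% response count, so such a subject is credited to DBS

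*Combined protocol and SAP*

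**What the plan says.** All references are to the combined protocol and SAP.

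- **Response (section 7.1).** "The primary outcome variable will be the clinical response of tic symptoms to treatment, as defined by a 40% decrease from baseline" in the YGTSS. Medication is not part of the definition.
- **Source of the cutoff (section 7.1).** "The cutoff of 40% was chosen to be consistent with the lower end of improvements observed in previous drug trials treating TS when compared to" (the sentence ends by naming placebo as the comparator).
- **Signal to go on (section 7.1).** "An improvement in at least one of the three participants is a potential indicator that DBS implantation" is worth pursuing further.
- **Medication in follow-up (section 4.1).** "Subjects will continue their pre-surgical psychiatric medications and any changes in medications will be documented at each study visit".
- **Visit procedures.** Section 4.10 says "Record changes in concomitant medications". Sections 4.7, 4.8, 4.9 and 4.14 contain the same item, and the table in section 4.12 marks medication monitoring at Visits 5 to 13.
- **Design (section 4.1).** Open label, one arm: "No blinding will be performed".
- **Statistical plan (section 7.4).** One sentence in full: "This is a pilot study looking at using DBS in 10 Tourette Syndrome patients".

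The rules for discontinuation (section 4.11) and early stopping (section 7.5) are not triggered by a medication change.

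**The concern.** The first primary objective (section 2.1) concerns the efficacy of DBS on tics. The count that answers it depends only on the YGTSS score, whatever else was done to the subject during a year of follow-up. The plan foresees medication changes and collects them, but gives them no role in the analysis. A subject who reaches the cutoff after a tic drug is started or raised therefore enters the count in the same way as one who reaches it on unchanged medication.

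No concurrent comparison is available to show how much of the fall the drug produced. The cutoff itself was set by reference to drug trials, so by the plan's own account drugs can produce changes of about this size.

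The reverse error is also possible: a drug reduced after DBS could mask a benefit. If the handling is left open, someone will have to decide which changes matter after seeing ten unblinded results.

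**Working it through.** The documents contain no power calculation, type I error rate, expected response rate or rate of medication change, so there is no figure of the plan's own to reproduce. The check is a reading of the rules, followed by arithmetic under stated assumptions.

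**1. Does any text remove or reclassify such a subject?** The response definition (7.1) has one condition, the YGTSS fall. The medication text (4.1 and the visit sections) has one consequence, recording. The statistical plan (7.4) has no rule for intercurrent medication and no sensitivity analysis. Sections 4.11 and 7.5 act on symptoms, tolerability and adverse events, not on drugs. The documents do not state in words that the subject counts as a responder. That follows because the only condition is met and nothing takes the subject out.

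**2. Effect of one subject on the rate.** With N = 10 (sections 2.1 and 7.4), R responders as defined and k of them reclassified, the supportive rate is (R − k)/10. Each reclassified subject lowers it by 1/10 = 10 percentage points. The documents give no basis for a value of k.

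**3. A drug need not supply the whole 40%.** Let d be the fall from DBS alone and r the further proportional fall of the remaining score from a drug. Response requires (1 − d)(1 − r) ≤ 0.60, so r ≥ 1 − 0.60/(1 − d).

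| d (assumed) | r needed |
|---|---|
| 20% | 1 − 0.60/0.80 = 25.0% |
| 30% | 1 − 0.60/0.70 = 14.3% |
| 37% | 1 − 0.60/0.63 = 4.8% |

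The 37% is the improvement between stimulation on and off that section 3.2 reports from a six-patient trial at this target. It is not a fall from baseline and serves only to mark the neighbourhood of the cutoff.

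**4. Chance of at least one responder from drug changes alone.** Let m be the share of subjects with a start or increase and q the chance that the change alone gives a 40% fall, so p = m × q. Assume no DBS effect and independent subjects. Then P(at least one of n) = 1 − (1 − p)^n. Both n = 3 and n = 10 are shown because section 7.1 refers to three participants and the rest of the plan to ten. That conflict is a separate matter.

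| p (assumed) | n = 3 | n = 10 |
|---|---|---|
| 0.02 | 5.9% | 18.3% |
| 0.05 | 14.3% | 40.1% |
| 0.10 | 27.1% | 65.1% |

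For example, m = 0.3 and q = 0.2 give p = 0.06, hence 16.9% for three subjects and 46.1% for ten. These figures show only that a signal resting on one subject is sensitive to this problem. They treat the improvement in the go-on sentence as a response, which section 7.1 does not say outright. They do not estimate what will happen.

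**The case against.** The case on the other side has four parts.

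**Continuity is the default.** Section 4.1 has subjects staying on their pre-surgical medication, with changes as the recorded exception. A reader might infer from the silence elsewhere that medication may change freely. The text does not support that: it can be read as an intention to hold medication stable. What it lacks is any consequence for the analysis when medication does change.

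**The entry criteria limit the threat.** Section 5.2 item 3 requires at least three failed adequate regimens, covering a typical neuroleptic, an atypical neuroleptic and a first-tier drug. Item 4 requires a behavioral trial, and item 6 requires care to be optimized over the preceding six months. A drug change that alone gives a 40% fall is therefore less likely than in an unselected population. This stands, and it reduces the likely size. But the criteria act before entry only, and having failed earlier drugs does not exclude a partial contribution near the cutoff (step 3).

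**Reclassifying does not isolate the DBS effect.** A reader might take the rate after removing these subjects as the DBS-attributable rate and quote, say, a drop from 40% to 20%. The documents support neither step. They give no response rate and no rate of medication change. Removing a subject with a drug increase assumes that DBS contributed nothing in that subject, which would be wrong for someone already well past 40% before a small late increase. Placebo response, and regression to the mean after a YGTSS entry threshold, stay in the count. A control arm would not settle the matter by itself either, unless medication changes were similar in both arms.

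**This is a small pilot with a modest claim, and the data are collected anyway.** That is true, and it is why a supportive analysis is enough. But data that are recorded without a rule permit only a choice made after the results are known.

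**Conclusion.** The gap is real and should be closed, though it does not invalidate the primary outcome. As written, a subject who crosses the cutoff after a tic drug is started or increased counts as a DBS responder. This conclusion rests on the definition in section 7.1 and the absence of any text that modifies it, not on an explicit statement.

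The size per subject is fixed by N = 10. The total is unknown and cannot be bounded from the documents. The entry criteria make large drug effects less likely and leave partial ones possible. The probabilities in step 4 depend entirely on assumed p.

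Any rule for these subjects also needs a baseline visit and an outcome visit. Section 7.1 names neither.

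**What to change.** Keep the primary responder definition. Add the following to section 7.1:

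1. **Visits.** Name the baseline visit used for the YGTSS and the visit at which response is judged.
2. **Supportive analysis.** Repeat the response count with a subject classed as a non-responder if a drug on the lists in section 5.2 item 3 was started or increased after the named baseline visit and the new drug or higher dose is still in use at the named outcome visit. The closed list avoids an unblinded judgement about why a drug was given. The still-in-use condition keeps a brief change that ended earlier from deciding the result.
3. **Listing.** For each subject, show all medication starts, increases and reductions, with dates, beside the YGTSS change. This covers reductions that may hide benefit and any drug outside the lists.
4. **Interpretation.** Describe the supportive rate as conservative under this rule, not as the rate attributable to DBS.

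This is an analysis rule only. It neither sets nor restricts anyone's medication.

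The cost is wording, since medication changes are already recorded and no visits or subjects are added. The downside is that the supportive rate may be lower than the primary one and may exclude some true DBS responders, including subjects given a listed drug for another reason.
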